### Adherence to Rebif Therapy:

The qualitative variables

- Injections been missed since last visit (Yes / No)
- Reason(s) for missed injections
  - Forgot to inject
  - Pain at injection site
  - Did not want injection
  - Injection site reaction other than pain
  - Flu like symptoms

- Fear of injection
- Fatigue
- Other

will be summarized for month 6 and month 12 as number and percentage from Safety Analysis Set.

The quantitative variable

- Estimated missed injections

will be summarized for month 6, month 12 and overall using descriptive statistics from Safety Analysis Set.

#### **Adherence Evaluation:**

Adherence (%) will be calculated for each subject as 100 x the number of injections the subject administered divided by the expected number of injections over 6 or 12 Months. If the subject terminates earlier than 12 months, the expected number of completed injections will be based on the subject's time on study.

The quantitative variable

- Adherence (%)

will be summarized for month 6 and month 12/End of treatment using descriptive statistics from Safety Analysis Set.

Adherence (%) = (No. of injections the subject administered / Expected No. of injections over 6 or 12 Months) x 100.

Number of injections the subject administered = Expected number of injections over 6 or 12 Months - Total No. of estimated missed injections since baseline visit.

The expected number of injections 3 times weekly (i.e. 3\*24 weeks (6 months) = 72 expected injections over 6 months and 144 expected number injections over 12 months).

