	
from Baseline to Month 6 and to Month 12.
 
Secondary Endpoints:
 
 
• ARR (after 12 months of Rebif treatment)
 
• Adherence (after 6 and 12 months of Rebif treatment)
 
• MusiQoL (compare Baseline with after 6 and 12 months of Rebif treatment)
 
• Reason/s for discontinuation of initial MS treatment (oral or injectable).
 
 
Additional Secondary Endpoints:
 
 
• Correlation between TSQM v II and ARR; TSQM v II and adherence; TSQM v II and reason for discontinuation
 
• Correlation between MusiQoL and ARR; MusiQoL and adherence; MusiQoL and reason for discontinuation
 
• Correlation between TSQM v II subscales and adherence
 
• Correlation between TSQM v II subscales and reasons for discontinuation
 
• Difference between TSQM v II subscales at Baseline and after 6 and 12 months of Rebif treatment
 
• ARR before study entry compared to ARR at study end
 
• Association between ARR and treatment adherence.
 

Study Design
	
This is a prospective, multicenter, open label, uncontrolled, non-interventional, single arm study to measure treatment satisfaction of RRMS patients on Rebif after discontinuing initial first-line treatment.
 
This study consists of three visits:
 
 
• Visit 1: Baseline
 

	
 
• Visit 2: Month 6
 
• Visit 3: Month 12
 
 
This study will enroll RRMS patients who have discontinued their oral or injectable first-line MS medication and have decided to initiate subcutaneous Interferon beta-1a (IFN <math>\beta</math> -1a) (Rebif) treatment before Baseline measurements. MusiQoL and TSQM v II will be measured at Baseline, Month 6 and Month 12. Relapses and adherence will be assessed at Month 6 and Month 12. Adherence to Rebif therapy will be collected electronically using RebiSmart 2.0.
 
Since this is a non-interventional study, there will not be any study required clinical interventions and laboratory assessments.

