### Exposure

[figure not shown]
Each patient will be observed for 12 months, during this period patients will receive Rebif 22 or 44 mcg three times per week through an electronic autoinjector device (Rebismart 2.0). The details of assessments are available in the flow chart given below.

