## 9. Changes to the Planned Analyses in the Observational Study Protocol

The statistical methods as described in the protocol were adopted. There are no changes to the planned analyses.

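### The adherence formula in SAP Section 16.2 does not use the electronic injector record named in the study design, and the source of the missed-injection estimate it uses is not stated

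*SAP*

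**What the plan says.** The SAP describes the adherence data in two ways and does not connect them.

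- **Section 6, Study Design:** "Adherence to Rebif therapy will be collected electronically using RebiSmart 2.0". The inclusion criteria require patients to be on Rebif through this device, and the Exposure text repeats that dosing is through it. The design therefore leads one to expect an electronic record for each patient.
- **Section 16.2, Adherence Evaluation:** "Adherence (%) = (No. of injections the subject administered / Expected No. of injections over 6 or 12 Months) x 100". The numerator is then defined as "Expected number of injections over 6 or 12 Months - Total No. of estimated missed injections since baseline visit". The expected number is fixed at "72 expected injections over 6 months and 144 expected number injections over 12 months". For patients who stop before 12 months it is based on time on study instead.
- **Section 16.2, Adherence to Rebif Therapy:** the variable "Estimated missed injections" stands beside a yes/no item on missed injections since the last visit and a list of reasons, such as forgetting or fear of injecting. No source is given for the count, and Section 16.2 does not mention RebiSmart.
- **Section 9:** "There are no changes to the planned analyses". The SAP therefore offers no explanation for the gap between Sections 6 and 16.2.

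**The concern.** The numerator is not a count of injections given. It is an assumed full schedule less an estimate of what was missed, so any miss absent from the estimate is scored as an injection given. The wording of the variable, and its place beside patient-type reasons, suggest recall at six-monthly visits, although the SAP does not say so.

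Adherence is a secondary objective and endpoint. It also enters the correlations with TSQM v II global satisfaction, with the TSQM v II subscales and with MusiQoL, and it is a candidate variable in the relapse regression. A reader who has seen the Study Design text would take all of these as resting on device-measured adherence.

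**Working it through.** **Inputs.** From SAP Section 16.2: 3 injections a week, 24 weeks for 6 months, and 72 and 144 expected injections. From the same section: time on study starts at first Rebif administration (defined under Annualized Relapse Rate), and misses are counted from the baseline visit. From Section 6: up to 6 months of Rebif before Visit 1. The share of true misses captured by the estimate, r, is not in the documents and is varied from 0% to 100% as an assumption. So is the true missed fraction, t.

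**Step 1: the plan's own figures.** 3 × 24 = 72, and 3 × 48 = 144. Both reproduce.

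**Step 2: effect of unreported misses.** With E expected injections and tE true misses, the plan returns 100 × (E − r·tE)/E = 100 × (1 − r·t). True adherence is 100 × (1 − t), so the excess is 100 × t × (1 − r). One unreported miss adds 100/72 = 1.39 points at 6 months or 100/144 = 0.69 points at 12 months.

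| True adherence | r = 100% | r = 75% | r = 50% | r = 0% |
|---|---|---|---|---|
| 95% | 95.0 | 96.25 | 97.5 | 100 |
| 90% | 90.0 | 92.5 | 95.0 | 100 |
| 80% | 80.0 | 85.0 | 90.0 | 100 |

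For one patient with 20 true misses out of 144, true adherence is 124/144 = 86.1%. If 10 are reported the plan gives 134/144 = 93.1%, and if none are it gives 100%.

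**Step 3: the denominator pulls the other way.** Six and twelve calendar months are about 26 and 52 weeks, that is 78 and 156 injections. If misses accrue over that time and all are reported, the plan returns 100 × (1 − t × 78/72). It then understates adherence by 0.4, 0.8 and 1.7 points at t = 5%, 10% and 20%. At t = 10%, 7.8/72 = 10.8%, so the result is 89.2% rather than 90%. The two effects cancel when r × 78/72 = 1, so net overstatement needs r below 72/78 = 92.3%. At t = 10% and r = 50% the net excess is 4.6 points rather than 5.0.

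**Step 4: early terminators.** If the Section 16.2 definition of time on study applies here, and first Rebif administration means the first ever, the expected count can include up to 6 months before Visit 1 while misses count only from baseline. Take a patient with 6 months of Rebif before Visit 1 who stops 6 months after it and misses 20% of 78 injections in the study, all reported. There are 15.6 misses and the expected count is 156. The plan gives 100 × (156 − 15.6)/156 = 90%, against 80% over the observed period. Every pre-baseline injection counts as given.

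**Step 5: associations.** If r is the same for all patients and above 0, plan adherence = 100 − r × (100 − true adherence), an exact linear rescaling. Pearson and Spearman coefficients do not change, and the regression slope per adherence point is multiplied by 1/r. Distortion of the correlations needs r to differ between patients.

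**The case against.** The strongest reply is that a bias has not been shown. The SAP cites a case report form that is not at hand. If site staff fill in the missed count from the device read-out, expected minus missed is just the complement of the device count, and nothing goes unreported. Asking for reasons does not settle the matter, since no device can supply them. An estimate can also be too high. This stands, and it rules out three stronger readings:

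- *That adherence is overstated, and always upward.* A reader might infer this from the formula. It requires the estimate to miss injections, which the SAP does not establish, and Step 3 shows a pull in the other direction.
- *That every association with adherence is weakened.* Step 5 shows that this does not follow. Uniform under-reporting leaves the correlations alone and makes the regression slope larger.
- *That Section 9 is wrong to declare no changes.* The protocol is not at hand and may itself specify estimated missed injections.

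It is also fair to say that adherence is a secondary endpoint, that the analyses are mainly descriptive, and that the SAP calls all tests explorative. None of this removes the mismatch. The SAP names an electronic source and then sets out a calculation that neither uses it nor says that the estimate comes from it.

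**Conclusion.** The point holds as a mismatch between the stated data source and the adherence calculation, together with an unstated source for the quantity that drives it. If the estimate is recall, the likely bias is upward, at 1.39 points per unreported miss at 6 months and 0.69 at 12 months. For true missed fractions of 5% to 20% and half of the misses reported, that is 2.5 to 10 points before the denominator offset. These ranges rest on assumed reporting shares and the actual size is unknown. If the estimate is read in full from the device, this mechanism adds nothing, and what remains is the 24/48-week denominator and the mismatched dates for early terminators. Associations with adherence may be distorted if under-reporting differs between patients. The change should be made: the endpoint is secondary, but the inconsistency is plain and the design already names a better source.

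**What to change.** In SAP Section 16.2, Adherence Evaluation:

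1. Define the numerator as the injections recorded by RebiSmart 2.0 from Visit 1 to the Month 6, Month 12 or end-of-study date.
2. Define the denominator as the injections expected over exactly the same dates, for completers and early terminators alike. It should not start at first Rebif administration, and it should not be a fixed 72 or 144. Changing only the numerator would create new errors. A fully adherent patient followed for 26 or 52 weeks would score 78/72 or 156/144 = 108.3%, and the fully adherent counterpart of the early terminator in Step 4 would score 78/156 = 50%.
3. Use this Adherence (%) in the TSQM v II, TSQM v II subscale and MusiQoL correlations and in the relapse regression.
4. State where the estimated missed injections come from. Keep them, with the reasons, as a supportive measure, or as a flagged fallback where no device log can be read.

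The cost is SAP wording and data import. The design says that adherence is collected electronically, but the SAP does not show that injection-level logs reach the study database, so this needs checking. Some logs may be unreadable or incomplete, and reported adherence may be lower.

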
Study Population and Eligibility Criteria
	
RRMS patients who have discontinued their initial MS treatment and for whom MS treatment is required according to the decision of the HCP and patient.
 
Inclusion Criteria:
 
The patient can be included when the patient
 
 
• Is male or female, 18 to 65 years of age (both inclusive), at the time of informed consent
 
• Is diagnosed with RRMS according to McDonald criteria 2010
 
• Has discontinued treatment with dimethyl fumarate (Tecfidera), teriflunomide (Aubagio), glatiramer acetate (Copaxone®), intramuscular IFN<math>\beta</math>-1a (Avonex®), pegylated interferon (Plegridy®), subcutaneous IFN<math>\beta</math>-1b (Betaferon®) or fingolimod (Gilenya®) within 6 months prior to Visit 1
 

- Is currently treated with Rebif using RebiSmart 2.0, for a maximum of 6 months prior to Visit 1
- Has a score on the Expanded Disability Status Scale (EDSS) between 0 to 5.0 inclusive
- Is willing and able to give informed consent.

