**Exclusion Criteria**

The patient cannot be included when the patient

- Has known planned surgical procedures at the time of the informed consent that will prevent adherence to treatment with Rebif through RebiSmart 2.0
- Is diagnosed with primary progressive, secondary progressive, or progressive relapsing MS
- Is pregnant or lactating, or planning to become pregnant
- In the opinion of the Investigator has significant renal or hepatic impairment or other significant disease (e.g., cognitive or visual impairment) that would compromise adherence and completion of the study
- Reports any reason that he/she cannot complete the 1 year study
- Has a history of hypersensitivity to natural or recombinant interferon, or any other component of the formulation
- Is contraindicated for the treatment with subcutaneous IFN $\beta$ -1a therapy as per summary of product characteristics or currently approved specific country product information
- Has any other factor that in the opinion of the Investigator would make the subject unsuitable for participation in this study

	
 
• Have significant psychiatric symptoms that, in the opinion of the Investigator, would impact patient ability to comply with treatment recommendations.
 

Study Size	133 patients diagnosed with RRMS will be enrolled (63 in the Netherlands, 40 in Switzerland and 30 in Belgium).
Sample size justification	A sample size of 106 subjects will be required to have 85% power to detect at least an 8 point difference in mean TSQM scores between Baseline and Month 6 or Month 12 measurements, with the standard deviation of 27.5 and a two sided significance level of 5%. Assuming a 20% drop out rate, approximately 133 patients will be enrolled into the study in the Netherlands, Switzerland and Belgium.

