## 16.2 Secondary Endpoint Analyses

### Annualized Relapse Rate (ARR):

The quantitative variables,

- Annualized Relapse Rate before study entry
- Number of relapses during the study
- Annualized Relapse Rate on study

will be summarized for prior MS Therapy categories and overall using descriptive statistics from Safety Analysis Set.

Annualized Relapse Rate before study entry = (No. of Relapses within 24 months prior to written informed consent / (30.4375\*24)) \* 365.25

Annualized Relapse Rate on study = (Sum of No. of Relapses at month 6 and month 12/ Time on Study) \* 365.25

where,

Time on Study (days) = (Date of Study Completion or Date of study discontinuation - Date of first Rebif administration +1)

95% Confidence Interval (CI) will also be provided for Annualized Relapse Rate before study entry and on study.

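### Expected injections of 72 and 144 rest on 24 and 48 weeks instead of 6 and 12 months, so completers who miss injections score too low; for early leavers the defined time on study does not match the window for missed injections

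*SAP*

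**What the plan says.** All references are to the SAP.

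- **Expected count.** Section 16.2, Adherence Evaluation, takes three injections per week, multiplies by 24 weeks for 6 months, and arrives at "72 expected injections over 6 months and 144 expected number injections over 12 months".
- **Administered count.** The same section does not count injections given. It derives them as "Expected number of injections over 6 or 12 Months - Total No. of estimated missed injections since baseline visit", and adherence is that number divided by the expected count.
- **Early leavers.** "If the subject terminates earlier than 12 months, the expected number of completed injections will be based on" the subject's time on study.
- **Length of observation.** Section 6, Exposure: "Each patient will be observed for 12 months". The exclusion criteria call it a one-year study: "Reports any reason that he/she cannot complete the 1 year study".
- **Month length.** The formula for the pre-study annualized relapse rate (ARR) in Section 16.2 divides by 24 months of 30.4375 days: "No. of Relapses within 24 months prior to written informed consent / (30.4375" and so on.
- **Time on study.** The only definition is given for the on-study ARR in Section 16.2. It ends at completion or discontinuation and counts from the first injection: "Date of study discontinuation - Date of first Rebif administration +1".
- **Rebif before baseline.** An inclusion criterion in Section 6 reads "Is currently treated with Rebif using RebiSmart 2.0, for a maximum of 6 months prior to Visit 1".

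**The concern.** Twelve months is about 52 weeks, not 48. A completer's missed injections accrue over the full interval from baseline to the visit. They are then subtracted from, and divided by, a count that covers only 48 weeks. Each missed injection therefore costs more than it should.

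For early leavers the mismatch runs the other way. If time on study has its defined meaning, the denominator can include up to 6 months before Visit 1, a period in which no miss is counted. Each missed injection then costs less than it should. Section 16.2 puts both groups into one summary for month 12 or end of treatment.

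Adherence is a named secondary endpoint. It also enters the correlations with the TSQM global score, the TSQM subscales and MusiQoL, and the regression of number of relapses.

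**Working it through.** **Inputs.** Three injections per week, 24 weeks for 6 months, and misses counted since baseline (Section 16.2, Adherence Evaluation); 30.4375 days per month (Section 16.2, ARR); 12-month observation and up to 6 months of earlier Rebif (Section 6).

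**1. The plan's own figures.** 3 × 24 = 72 and 3 × 48 = 144. Both reproduce.

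**2. Expected counts on the SAP's month length.**
- 6 months: 6 × 30.4375 = 182.625 days; 3 × 182.625 / 7 = 78.3.
- 12 months: 12 × 30.4375 = 365.25 days; 3 × 365.25 / 7 = 156.5.
- Shortfall: 1 − 144 / 156.54 = 8.0%, and the same at 6 months. Against 26 and 52 weeks: 1 − 144 / 156 = 7.7%.

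**3. Effect on a completer.** The SAP score is 100 × (144 − missed) / 144. With 156.54 injections due and true adherence A (in %), missed = 156.54 × (100 − A) / 100. The score becomes 100 − (156.54 / 144) × (100 − A) = 100 − 1.087 × (100 − A). The ratio is the same at month 6.

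| True adherence | SAP score | Under-scored by (points) | Against 52 weeks (points) |
|---|---|---|---|
| 100% | 100.0% | 0 | 0 |
| 95% | 94.6% | 0.4 | 0.4 |
| 90% | 89.1% | 0.9 | 0.8 |
| 80% | 78.3% | 1.7 | 1.7 |
| 50% | 45.7% | 4.4 | 4.2 |

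At the extreme, 150 missed injections give 100 × (144 − 150) / 144 = −4.2%, although about 156 fall due in a year.

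**4. Effect on an early leaver under the SAP's definition of time on study.** Assumed case: exit 9 months after Visit 1, true adherence 90%, and k months of Rebif before Visit 1. Expected injections are taken as three per week of time on study; the extra day in the definition is ignored.
- Due since Visit 1: 3 × 9 × 30.4375 / 7 = 117.4. Missed: 0.10 × 117.4 = 11.74.
- Expected from first Rebif: 3 × (9 + k) × 30.4375 / 7.
- Score: 100 × (1 − 0.10 × 9 / (9 + k)).

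| Earlier Rebif, k (months) | Expected | Score |
|---|---|---|
| 0 (same as a Visit 1 start) | 117.4 | 90.0% |
| 1 | 130.4 | 91.0% |
| 3 | 156.5 | 92.5% |
| 6 | 195.7 | 94.0% |

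A completer at the same true 90% is scored 89.1%. On this reading two equally adherent subjects can differ by up to 94.0 − 89.1 = 4.9 points.

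**The case against.** **The 8.0% figure invites too much.** A reader might infer that adherence is wrong by 8%, or that every completer is under-scored. Neither follows. Administered injections are expected minus missed, so a subject with no misses scores 100% on either denominator, and the error is under one point at 90% adherence or better. This stands.

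**The size is nominal.** The 30.4375-day month annualizes a relapse look-back and does not schedule visits; the SAP shows no visit windows. This stands for the size in any one subject, which depends on actual visit dates. It does not remove the direction: the SAP itself calls the observation 12 months and one year, and 26 and 52 weeks give nearly the same result.

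**The leaver rule has a rate and a start date.** A reader might infer that the rule gives neither. The section does state three times weekly, which is the direct conversion, and Section 16.2 does define time on study. A pro rata share of 144 is possible, but it is a construction that the text does not call for. The defect is therefore the mismatch between a period that starts at first Rebif and misses that start at baseline. What remains open is whether that definition is meant: the adherence text uses the term in lower case without a cross-reference, and its baseline anchor for misses could point to Visit 1.

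**Consequences are limited.** Section 11 declares all tests exploratory, and the missed counts are themselves estimates. Among completers with equal follow-up the error is a linear rescaling, so it leaves correlations unchanged. This stands and limits the severity.

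**Conclusion.** The point holds, at minor to moderate severity.

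The constants 72 and 144 are wrong against the SAP's own description of the study: 8.0% short on its month length. Completers who miss injections are scored too low, nominally by 0.4 points at 95% true adherence, 0.9 at 90%, 1.7 at 80% and 4.4 at 50%. These sizes assume assessments at 182.6 and 365.25 days.

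For early leavers the result depends on what time on study means. Under the only definition in the SAP, those with Rebif before Visit 1 are scored too high; the 91.0 to 94.0% range rests on the assumed month-9 exit at true 90%. If a Visit 1 start is meant, this inflation disappears, but the section should say so. The sample size allows for a 20% drop-out, which is 133 − 106 = 27 subjects. How many would have a usable missed-injection count is not shown.

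The effect is confined to the descriptive adherence endpoint and the exploratory analyses that use it. A reader might infer that the TSQM result is at risk; it is not, because the primary paired comparison does not use adherence.

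**What to change.** In Section 16.2, Adherence Evaluation:

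1. Delete the fixed 72 and 144.
2. For every subject, completer or leaver, set expected injections = 3 × (days from Visit 1 to the assessment or discontinuation date) / 7, using the frequency that the SAP already states.
3. Count missed injections over that same window.
4. State that this interval is not the Time on Study used for the ARR.

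The cost is a few lines of SAP text and a small programming change that uses visit and discontinuation dates. The one thing to check is whether the case report form, which is not shown, captures missed injections up to a leaver's exit date.
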